I have read and understand the contents of this clinical protocol for Study No. KCP-9274-901 dated 11 March 2020 and will adhere to the study requirements as presented, including all statements regarding confidentiality. In addition, I will conduct the Study in accordance with current Good Clinical Practice, ICH E6, and applicable FDA regulatory requirements.

Printed Name of Investigator

[figure not shown]
Signature of Investigator

Institution

Date

PROTOCOL SYNOPSIS

Sponsor: Karyopharm Therapeutics Inc.	Investigational Product: KPT-9274	Study Phase: Phase 1
Title of Study: A Phase 1 Open-Label Study of the Safety, Tolerability and Efficacy of KPT-9274, a Dual Inhibitor of PAK4 and NAMPT, in Patients with Advanced Solid Malignancies or Non-Hodgkin's Lymphoma		
Study Name: PANAMA: PAK4 and NAMPT in Patients with Solid Malignancies or NHL		
Name of Active Ingredient: (E)-3-(6-aminopyridin-3-yl)-N-((5-(4-(4,4-difluoropiperidine-1-carbonyl)phenyl)-7-(4-fluorophenyl)benzofuran-2-yl)methyl)acrylamide		
Protocol Number: KCP-9274-901		
Study Center(s): Multi-center		
Patient Population: Patients with advanced solid malignancies (including sarcoma, colon, lung, etc.) or non-Hodgkin's lymphoma for which all standard therapeutic options considered useful by the investigator have been exhausted and with progressive disease on study entry.		
Objectives and Endpoints: This study will evaluate the safety, tolerability, and efficacy of oral KPT-9274 for the treatment of patients with advanced solid malignancies or non-Hodgkin's lymphoma (NHL).		
Objectives	Endpoints	
Primary		
Parts A and B 
• To assess the maximum tolerated dose (MTD) in each Part• To establish a recommended phase 2 dose (RP2D)	Parts A and B 
• MTD/RP2D• Dose limiting toxicities (DLTs)• The occurrence of Grade ≥ 3 adverse events (AE), all serious adverse events (SAEs), and all AEs leading to treatment discontinuation	
Dose Expansion (if conducted) 
• Preliminary evidence of anti-tumor activity of KPT-9274 at the RP2D \pm niacin ER	Dose Expansion (if conducted) 
• Overall response rate (ORR), duration of response (DOR), disease control rate (DCR), duration of disease control, progression-free survival (PFS), overall survival (OS), time to progression (TPP)	

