1.2.1. Potential Risks

As of 02 March 2019, 47 patients had received KPT-9274 alone or with niacin ER in Parts A and B of this study. Dose levels and schedules are outlined in [Table 10](#), along with the number of patients enrolled in each cohort. The most common AEs occurring across all patients in Parts A and B, were anemia (68%), nausea (34%), arthralgia (32%), fatigue (32%), and myalgia (23%) ([Table 11](#); [Table 12](#)). AEs were largely dose dependent and increased with higher doses of KPT-9274. There were 2 DLTs reported among the first 47 patients. These included one case of grade 4 anemia, which occurred in the 40 mg KPT-9274 qodX3 cohort, and one case of grade 3 fatigue which occurred in the 80 mg KPT-9274 qodX3 + niacin cohort. Both dose levels enrolled

additional patients per the 3+3 study design, and both dose levels ultimately cleared DLT evaluation. To date, a MTD has not been reached.

Table 10: Dose Levels and Schedules Tested as of 02 March 2019

Cohort	Dose / Schedule	Patients Enrolled
1	10 mg / qodx3	3
2	20 mg / qodx3	3
3	30 mg / qodx3	5
4	40 mg / qodx3	7
5	40 mg / qodx2	5
3B	30 mg / qodx3 + 500 mg niacin ER	3
4B	40 mg / qodx3 + 500 mg niacin ER	4
5B	60 mg / qodx3 + 500 mg niacin ER	10
6B	80 mg / qodx3 + 500 mg niacin ER	6
7B	100 mg / qodx3 + 500 mg niacin ER	1

Table 11: Treatment Related Adverse Events Occuring in $\geq 10\%$ of All Patients

Adverse Events	All Dose Levels (N=47)				
	G1	G2	G3	G4	Total
Anemia	2	7	22	1	32 (68%)
Nausea	13	3			16 (34%)
Arthralgia	11	4			15 (32%)
Fatigue	7	6	2		15 (32%)
Myalgia	7	4			11 (23%)
Diarrhea	6	3	1		10 (21%)

Vomiting	7	1	1		9 (19%)
Dyspnea	4	2	2		8 (17%)
AST increase	2	3			5 (11%)
Peripheral edema	3	2			5 (11%)

Table 12: Treatment Related Adverse Events Occuring in $\geq 10\%$ of Patients by Dose Level and Schedule

10 mg (N=3)		20 mg (N=3)		30 mg (N=5)		30 mg + Niacin (N=3)		40 mg (N=7)		40 mg + Niacin (N=4)		40 mg BIW (N=5)		60 mg + Niacin (N=11)		80 mg + Niacin (N=5)		100 mg + Niacin (N=1)		
All	G1/2	G3+	G1/2	G3+	G1/2	G3+	G1/2	G3+	G1/2	G3+	G1/2	G3+	G1/2	G3+	G1/2	G3+	G1/2	G3+	G1/2	G3+
	1	1	1	2	1			6		2	3	2	2	5	1	4			1	
								3		3		1		5		3		1		
			2		2		5		1		1		2		1		1			
				1	1	1		2		1		2		4		2	1			
	1		2		1		1		1		2		2					1		
			1		1		2				1	1	1		2		1			
							1		2					2	1	2		1		
							1		1	1				1	1	3				
				1		1			1		1			1						
	1		1				1							1		1				
			2		1									1						
					1		1							1		1				
							2								1				1	

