6.2.6.2. Dose-Limiting Toxicity

A DLT is defined as an AE or abnormal laboratory value that occurs within the first 28 days of treatment with KPT-9274, except for those that are clearly and incontrovertibly due to underlying disease, disease progression, or extraneous causes, and meets any of the criteria included in [Table 14](#). The CTCAE, Version 4.03 will be used for grading. In addition, > 3 missed (consecutive or non-consecutive) doses of KPT-9274 in the first 28 days due to a drug related toxicity will be considered to be a DLT.

Other events may occur which do not meet the definition of a DLT, but are of concern to the Investigators and Karyopharm, and may then be considered to be DLTs.

Table 14: Criteria for Defining Dose-Limiting Toxicities

Toxicity	Any of the following criteria (based on CTCAE [Version 4.03]):
Non-Hematologic	Grade \geq 3 nausea/vomiting, dehydration or diarrhea while taking optimal supportive medications.
	Any other Grade \geq 3 non-hematological toxicity except alopecia or electrolyte abnormalities correctable with supportive therapy.
Hematologic	Grade 4 neutropenia lasting more than 5 days.
	Febrile neutropenia of any duration (ANC $< 1.0 \times 10^9$ with single temperature $> 38.3^{\circ}\text{C}$ or a sustained temperature $\geq 38^{\circ}\text{C}$ for more than 1 hour).
	Grade 4 thrombocytopenia, or Grade 3 thrombocytopenia with bleeding, or any requirement for platelet transfusion.
	Grade 4 anemia, unexplained by underlying disease.

CTCAE Version 4.03 will be used for grading AEs and laboratory abnormalities. Patients may receive supportive care as per local institutional guidelines.

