6.2.6.3. Dose Decision Meeting or Teleconference

To implement dose escalation decisions, available toxicity information (including all AEs and all laboratory abnormalities regardless of DLT assessment) will be evaluated by the enrolling Investigators and Karyopharm study personnel during a dose decision meeting or teleconference. Decisions will be based on an evaluation of all relevant data available from all dose cohorts evaluated in the ongoing study including safety information, DLTs, all NCI CTCAE (Version 4.03), toxicity data during Cycle 1 and PK data (if available) from evaluable patients.

Drug administration at the next higher dose cohort may not proceed until the Investigator receives written confirmation from Karyopharm indicating that the results of the previous dose cohort were evaluated and that it is permissible to proceed to the next higher dose cohort.

Interim safety data will be examined on an ongoing basis to ensure patient safety and to comply with the clinical study dose escalation rules (see Section 9.8). In addition, Karyopharm will conduct regular safety meetings with investigators and other site staff where all AEs are shared across the study, and appropriate management of toxicities fully reviewed and, as needed, implemented.

6.2.7. Dose Schedule for Evaluation During the Dose Expansion Phase (Parts A and B)

After completion of the Dose Escalation Parts A and B, Dose Expansion in up to 65 additional patients with advanced solid malignancies and NHL may be conducted to further explore safety, tolerability and preliminary evidence of anti-tumor activity of the RP2D of KPT-9274 ± niacin ER. Note that preliminary clinical results may define the patient population (i.e., specific indications) selected for enrollment in the Dose Expansion Phase.

After declaring the RP2D for KPT-9274 single agent and KPT-9274 + niacin ER, based on the safety and tolerability results of the Dose Escalation Phase, a decision will be made whether expansion (4 groups, ~45 patients total) will be conducted at the RP2D of KPT-9274 single agent or at the RP2D of KPT-9274 + niacin ER. If the ~45 patient expansion is conducted at the RP2D of KPT-9274 + niacin ER, an optional expansion with < 20 patients at the RP2D of KPT-9274 single agent may also be initiated.

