6.9. Supportive Care, Contraception Requirements, and Concomitant Medications

6.9.1. Supportive Care

Patients are expected to be aggressively treated to minimize the likelihood and/or severity of side effects at the discretion of the Investigator (consultation with the Karyopharm Medical Monitor is strongly encouraged), including hematologic and musculoskeletal (arthralgias and myalgias) symptoms observed in humans.

Supportive care including anti-nausea/anti-emetic therapy, acid suppression (e.g., PPIs \pm H2 blockers), anti-diarrheal therapy, and other standard treatments may be administered as per institutional guidelines for symptomatic patients. For additional options, please see NCCN Supportive Care Clinical Practice Guidelines in Oncology. Note: the use of PPIs is allowed in all patients but the Investigator must consult with the Karyopharm Medical Monitor prior to their use in patients receiving niacin ER. If any deficiencies in vitamin B12, folate, iron, erythropoietin, or transferrin are observed, then standard medical practice for their replacement should be instituted.

Anemia appears to be dose dependent and should be treated with dose interruption, dose reduction, use of growth factors (i.e., erythropoietins), and/or transfusions. The addition of niacin ER (up to 2,000 mg daily dose, per label) will be allowed after completion of the DLT period in cycle 1 (first 28 days) in an attempt to offset potential side effect (i.e. anemia, arthralgias, myalgias, etc.) of KPT-9274. After Week 8, niacin may be titrated, as per label, to patient response and tolerance. If response to 1000 mg daily is inadequate, increase dose to 1500 mg daily; may subsequently increase dose to 2000 mg daily. Daily dose should not be increased more than 500 mg in a 4-week period, and doses above 2000 mg daily are not recommended. Women may respond at lower doses than men.

Arthralgia should be treated with non-steroidal anti-inflammatory drug (NSAIDs), cyclooxygenase-2 (COX-2) inhibitors, acetaminophen, tramadol, and/or low-dose steroids. Myalgia and flu-like illness should be treated with KPT-9274 dosing at night, acetaminophen (including pre-treatment with acetaminophen), NSAIDs, COX-2 inhibitors, and/or low-dose steroids. Consultation with the Karyopharm Medical Monitor is recommended for questions regarding these recommendations.

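### Table 14's anemia row has its own cause filter with no certainty standard, so a Cycle 1 Grade 4 anemia that the general DLT exclusion would count may be left out of the 3+3 count

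*Protocol*

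**What the plan says.** Protocol 6.2.6.2 defines a DLT as an adverse event or laboratory abnormality in the first 28 days that meets a Table 14 criterion, "except for those that are clearly and incontrovertibly due to underlying disease, disease progression, or extraneous causes". That exclusion applies to the whole table. The anemia row then reads "Grade 4 anemia, unexplained by underlying disease". The synopsis table of DLT criteria has the same row.

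Two further routes to a DLT lie outside the table, in the same section:

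- **Mandatory.** More than 3 KPT-9274 doses missed in the first 28 days because of a drug-related toxicity is a DLT.
- **Discretionary.** Events may fall outside the definition "but are of concern to the Investigators and Karyopharm, and may then be considered to be DLTs".

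Section 6.2.6.1 turns the DLT count into the escalation decision and the MTD. Under 6.2.8, a patient with a Cycle 1 DLT in the escalation phase must stop KPT-9274. A Grade 3 or higher anemia that is not a DLT falls under Table 16, where holding the drug is only to be considered. Dosing may continue unchanged, with transfusion or growth factor support, after consultation with the Medical Monitor. Part C uses the same DLT definition (3.1).

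**The concern.** Two attribution tests apply to anemia and one applies to everything else. The general test is strict: the event counts unless disease is beyond dispute as the cause. The anemia test has no stated strictness, and an event must pass both tests. The work-up in 7.5.3 and 7.5.4.2 helps to find a cause but sets no threshold for calling an anemia explained. Two investigators with the same results could therefore classify the same event differently.

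The row concerns the drug's leading toxicity. Section 6.9.1 says: "Anemia appears to be dose dependent and should be treated with dose interruption, dose reduction, use of growth factors". Part A and B patients enter with progressive advanced cancer, so a disease explanation will often be arguable. They must also enter with hemoglobin of at least 10.0 g/dL (4.2), so a Grade 4 anemia in Cycle 1 is a marked fall on treatment. At stake are the DLT count, the MTD built on it, and whether the patient concerned must stop or may continue.

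**Working it through.** **1. Compare the rows.** Table 14 has six rows. Five limit by grade, duration, fever, bleeding or platelet transfusion, supportive care, or event type. None of those five limits by cause. Only the anemia row does.

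**2. What the extra filter can do.** Take a Grade 4 anemia that survives the general exclusion, so disease is not incontrovertibly the cause.

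- If the row's filter means incontrovertibly explained, it removes nothing further and is redundant.
- If it means probably or plausibly explained, it removes events that the general exclusion would keep.

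No reading adds an event, so the filter can only leave the DLT count unchanged or lower it.

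**3. Where an event that fails the row goes.** DLT evaluability needs at least 9 of 12 doses (6.2.6.1), so at most 12 − 9 = 3 missed. If the catch-all is not used:

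| Cycle 1 doses missed | Cause as judged | Result |
|---|---|---|
| 3 or fewer | any | evaluable, counted as a non-DLT |
| more than 3 | drug related | DLT, mandatory |
| more than 3 | not drug related | non-evaluable; replacement considered (3.2) |

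The second line depends on Table 20, where an event is related if the drug is the more likely explanation. A probably disease-related anemia may not meet that. Because Table 16 makes holding optional, the threshold of more than 3 missed doses may also never be reached.

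**4. Observed frequency.** Table 11 lists treatment-related events in 47 patients. Anemia: Grade 3 in 22, Grade 4 in 1, total 32.

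- Any grade: 32/47 = 68.1%.
- Grade 3 or 4: (22 + 1)/47 = 48.9%, of which 22 of 23 are Grade 3 and outside this row under any wording.
- Grade 4: 1/47 = 2.1% (exact 95% CI 0.05% to 11.3%).

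Section 1.2.1 says of the two DLTs reported: "These included one case of grade 4 anemia, which occurred in the 40 mg KPT-9274 qodX3 cohort". I take this to be the Grade 4 case in Table 11. It was counted, and 40 mg still cleared.

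**5. The plan's own figure.** Section 9.8 gives a 0.57 probability of halting at a cohort when the DLT rate is 33%. With q = 1 − p, P(halt) = 1 − [q³ + 3pq² × q³]. At p = 0.33 this is 1 − [0.3008 + 0.4444 × 0.3008] = 0.566; at p = 1/3 it is 0.572. Both round to 0.57.

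**6. One disputed event under the 3+3 rule.** This covers the first line of the table in step 3: a patient who missed no more than 3 doses. P(escalate) is under the written rule, before the dose meeting's discretion, with q³ = 0.301, 0.512 and 0.729 at p = 0.33, 0.20 and 0.10. The 0.33 is the protocol's figure; 0.20 and 0.10 are assumed.

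| Situation | Event counted | Event not counted |
|---|---|---|
| First three, no other DLT | q³ = 0.30 / 0.51 / 0.73 | 1 |
| First three, one other DLT | 0 | q³ = 0.30 / 0.51 / 0.73 |
| Second three after 1 of 3, no other DLT | 0 (2 of 6) | 1 (1 of 6) |

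These are consequences of reclassifying any single event in a 3+3. They are not a rate at which this wording would cause it.

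**The case against.** **The missed-dose rule is mandatory.** A reader might infer that an anemia failing the row becomes a DLT only if the catch-all is used. The documents do not support that, because more than 3 doses missed for a drug-related toxicity is a DLT regardless. This objection stands, and the conclusion is limited accordingly. The rule narrows the gap but does not close it, for the reasons in step 3.

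**The row need not be read loosely.** It asks whether the anemia is unexplained, and a merely possible disease explanation is arguably not an explanation. The row can also be read in harmony with the general exclusion. This stands as well: the text is ambiguous and does not compel the looser reading. On the harmonised reading, however, the extra words do no work.

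**The headline anemia figures miss the target.** A reader might take 68% or 49% as the size of the problem. They are not. They describe treatment-related anemia, are not confined to Cycle 1, and are almost all below Grade 4.

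**Escalation is a joint decision.** At the dose meeting, "available toxicity information (including all AEs and all laboratory abnormalities regardless of DLT assessment) will be evaluated by the enrolling Investigators" and sponsor personnel, and written sponsor confirmation is needed before the next dose. The event also enters the Grade 3 or higher primary safety endpoint, and Part C's RP2D rests on a committee review of all data. These are real safeguards. They do not change the count by which Parts A and B define the MTD.

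**The qualifier may be deliberate.** Some NHL patients may have marrow involvement, where anemia from disease is expected. That is a fair reason for care, but the general exclusion already removes the clear cases. It is also true that the general standard is itself a judgement, so deleting the filter makes attribution uniform without making it automatic.

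**Conclusion.** The anemia row is the only DLT row with its own cause filter, and it sets no certainty standard. The filter is either redundant or looser than the exclusion that already governs the table, and on the looser reading it can only lower the DLT count, which pushes towards too high an MTD. A Cycle 1 Grade 4 anemia that disease probably but not incontrovertibly explains may therefore go uncounted, unless the missed-dose rule or the catch-all brings it back.

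The size cannot be given as an average effect. Table 11 covers treatment-related events only, so the documents give no rate for Grade 4 anemia attributed to disease. It would go too far to infer that a dose decision has already been distorted: the one Grade 4 anemia reported was counted, and no past decision is shown to change. What remains is the leverage of a single event in cohorts of 3 or 6, as worked above. It rests on the looser reading being applied, on no more than 3 missed doses, and on the written rule being followed. This is a cheap improvement that the sponsor could make, not a flaw that undermines the study.

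**What to change.** In Table 14 (6.2.6.2) and in the matching synopsis table, delete the cause qualifier so that the row specifies Grade 4 anemia and nothing more. The general exclusion then governs attribution for anemia as it does for every other row, and incontrovertibly disease-related anemia stays excluded. The missed-dose rule, the catch-all, section 6.2.8 and the SAP need no change.

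The edit is four words in two places. Its downside is that a few probably disease-related Grade 4 anemias will count as DLTs. Each can add 3 patients to a cohort or stop escalation one level earlier, and those patients must discontinue KPT-9274.

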6.2.6.3. Dose Decision Meeting or Teleconference

To implement dose escalation decisions, available toxicity information (including all AEs and all laboratory abnormalities regardless of DLT assessment) will be evaluated by the enrolling Investigators and Karyopharm study personnel during a dose decision meeting or teleconference. Decisions will be based on an evaluation of all relevant data available from all dose cohorts evaluated in the ongoing study including safety information, DLTs, all NCI CTCAE (Version 4.03), toxicity data during Cycle 1 and PK data (if available) from evaluable patients.

Drug administration at the next higher dose cohort may not proceed until the Investigator receives written confirmation from Karyopharm indicating that the results of the previous dose cohort were evaluated and that it is permissible to proceed to the next higher dose cohort.

Interim safety data will be examined on an ongoing basis to ensure patient safety and to comply with the clinical study dose escalation rules (see Section 9.8). In addition, Karyopharm will conduct regular safety meetings with investigators and other site staff where all AEs are shared across the study, and appropriate management of toxicities fully reviewed and, as needed, implemented.

6.2.7. Dose Schedule for Evaluation During the Dose Expansion Phase (Parts A and B)

After completion of the Dose Escalation Parts A and B, Dose Expansion in up to 65 additional patients with advanced solid malignancies and NHL may be conducted to further explore safety, tolerability and preliminary evidence of anti-tumor activity of the RP2D of KPT-9274 ± niacin ER. Note that preliminary clinical results may define the patient population (i.e., specific indications) selected for enrollment in the Dose Expansion Phase.

After declaring the RP2D for KPT-9274 single agent and KPT-9274 + niacin ER, based on the safety and tolerability results of the Dose Escalation Phase, a decision will be made whether expansion (4 groups, ~45 patients total) will be conducted at the RP2D of KPT-9274 single agent or at the RP2D of KPT-9274 + niacin ER. If the ~45 patient expansion is conducted at the RP2D of KPT-9274 + niacin ER, an optional expansion with < 20 patients at the RP2D of KPT-9274 single agent may also be initiated.

At least 1 clinical response (minimum of stable disease ~8 weeks) must be seen in any of the first ten patients treated at the RP2D in order to fully enroll either expansion cohort. These 10 patients include the patients enrolled under the 3+3 design for DLT assessment; if necessary, additional patients will be enrolled to a maximum of 10 patients. If no clinical responses are observed, the study will be stopped for futility. If a clinical response is observed at any time, then enrollment of the full expansion cohort may proceed. Initiation of the KPT-9274 + niacin ER escalation will not be dependent upon demonstration of clinical benefit of the single agent, but futility at the KPT-9274 + niacin ER RP2D will be assessed prior to full expansion using the same criterion as described above for the single agent KPT-9274.

The KPT-9274 ± niacin ER expansion cohort will consist of 4 groups of approximately 45 patients (please note that these expansion groups may change based on escalation results) including:

- NAPRT1 deficient tumor group, approximately 10 patients
- NAPRT1 positive tumor group, approximately 10 patients
- Either NAPRT1 deficient or positive tumor group, approximately 10 patients
- IDH1 mutant tumor group, approximately 15 patients

Please note that the composition of the expansion groups (e.g. number of patients with NAPRT1 positive vs NAPRT1 deficient tumors) may change based on the results from the escalation phase.

An additional, optional KPT-9274 single agent expansion cohort will consist of < 20 patients with any tumor mutational status.

Patients in the Dose Expansion Phase may be treated with the RP2D of KPT-9274 ± niacin ER according to the same schedule administered in the Dose Escalation Phase of the study.

Patients who are in Part A or Part B of the Dose Escalation Phase being treated at the RP2D ± niacin ER dose chosen for expansion will be included in the efficacy and safety analyses of the Dose Expansion Phase.

